10.4 Secondary Statistical Endpoints

No hypothesis testing will be performed for secondary endpoints.

10.4.1 Secondary Safety Endpoints

Rates for all-cause mortality, AAA related mortality, major adverse events, AAA rupture, and surgical conversion will all be calculated at 30 days and 12 months. The Kaplan-Meier estimates will be presented with 95% confidence intervals.

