8.7 Imaging Core Lab

TriVascular will utilize an independent imaging Core Lab to analyze device performance specifically related to study endpoints such as: device integrity, endoleaks, migration, and aneurysm dimensions (e.g., length, diameter, volume). Clinical sites will submit all CT and X-ray images to the Core Lab for all required study visits.

Study Visit	Images* Required to be submitted to Core lab
Baseline (pre-op)	Contrast Enhanced Spiral Abdominal/Pelvic CT
Discharge (post-op)	Abdominal X-rays (AP, lateral, left oblique and right oblique views)
1 month (16 - 44 days)	Abdominal X-rays (AP, lateral, left oblique and right oblique views) Contrast Enhanced Spiral Abdominal/Pelvic CT
6 month (150 - 210 days)	Abdominal X-rays (AP, lateral, left oblique and right oblique views) Contrast Enhanced Spiral Abdominal/Pelvic CT
12 month (305 - 425 days)	Abdominal X-rays (AP, lateral, left oblique and right oblique views) Contrast Enhanced Spiral Abdominal/Pelvic CT

*Refer to **Appendix VI: CT Scanning Techniques** and Manual of Operations for Core Lab imaging requirements.

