8.13 Conversion to Open Surgical repair

Conversion to open surgical repair may occur either at the initial implant procedure or subsequent to the initial procedure. Information regarding the surgical conversion will be recorded on the Open Surgical **Conversion eCRF** and the **Adverse Event eCRF**.

In the event that a subject requires conversion from endovascular to open surgical repair, the explanted device should be sent to TriVascular for examination. Refer to the Manual of

Operations for specific instructions for managing the removal, shipping and handling of the explanted device. Explant information will be recorded on the **Explant eCRF**.

Surgical conversions must be reported by telephone or fax to the Sponsor **within 24 hours** of knowledge of the event.

The Follow-up visit schedule for surgically converted subjects is at one month and one year post open conversion.

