9.0 ENDPOINTS AND TECHNIQUES FOR MEASUREMENT

For the purpose of this study, the information below provides definitions and measurement criteria in determining each endpoint. The endpoints (primary and secondary) specified below and Statistical Considerations outlined in Section 10 may appear in the product labeling to support clinical results. Information not included in the endpoint list below or the statistical considerations will not appear in the labeling to support clinical results.

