10.2 Statistical Sample Size Justifications for the Primary Study Phase

Should the rate of major adverse events be 11%, n=150 primary study subjects would provide 96% power to test the primary safety hypothesis at the one-sided 5% significance level.

It is anticipated that attrition through the 12 month visit may be approximately 15%. Hence 150 primary study subjects less 15% attrition would yield approximately 130 subjects with data available to assess the primary effectiveness endpoint at 12 months. Should the rate for the primary effectiveness composite endpoint equal 88.2%, then 130 subjects would provide 80% power to test the primary effectiveness hypothesis at the one-sided 0.05 alpha level. Sample size calculations were performed using the normal approximation in nQuery Advisor 6.02.

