10.9 Detailed Statistical Analysis Plan

Prior to database lock a detailed statistical analysis plan will be written to provide a detailed description of the statistical analysis to be used in the final analysis. This plan will incorporate lists of relevant variables to be included in multiple imputations analysis and will incorporate any protocol changes that would affect the analysis.

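### Does Section 10.4.1 need a rule for the 95% interval when a secondary safety endpoint has no events?

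*Combined protocol and SAP*

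**What the plan says.** Section 10.4.1 covers five endpoints at two time points: "Rates for all-cause mortality, AAA related mortality, major adverse events, AAA rupture, and surgical conversion will all be calculated at 30 days and 12 months". On precision it adds only that "The Kaplan-Meier estimates will be presented with 95% confidence intervals". It does not name Greenwood's variance, a transformation, or a convention for a time point with no events.

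Two other sections set the weight of this. Section 10.4 states that "No hypothesis testing will be performed for secondary endpoints", so the intervals are descriptive. Section 10.9 makes this commitment: "Prior to database lock a detailed statistical analysis plan will be written to provide a detailed description of the statistical analysis". That section mentions multiple-imputation variables and protocol changes but not interval methods.

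Sections 10.3.1 and 10.3.2 give closed-form limits for the two primary endpoints only. Section 9.0 says that the primary and secondary endpoints "may appear in the product labeling to support clinical results".

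**The concern.** Rupture and conversion could be rare enough for the study to record none. The Kaplan-Meier estimate is then 100% event-free, and the usual Greenwood variance is zero. An interval built on it either has no width or cannot be computed. A table showing 0% (95% CI 0% to 0%) for rupture, the outcome that repair is meant to prevent, would claim certainty that 150 subjects cannot give. With no tests on these endpoints, the estimate and its interval carry all the information, and they may reach the labeling. Nothing in the current text prevents this, and a method chosen after a zero has been seen would be post hoc.

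**Working it through.** **Plan's own figures.** The plan gives none for these intervals. Its nearest figures, the powers in Section 10.2, reproduce with the one-sample normal approximation, power = Φ[(|p0 − p1| − 1.645·√(p0(1−p0)/n)) / √(p1(1−p1)/n)]:

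- Safety (n = 150, 11% against 21%): (0.10 − 1.645 × 0.03326)/0.02555 = 1.773, power 96.2% (stated 96%).
- Effectiveness (n = 130, 88.2% against 80%): (0.082 − 1.645 × 0.03508)/0.02830 = 0.858, power 80.5% (stated 80%).

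Neither uses a secondary safety interval.

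**Behaviour at zero events.** Greenwood's sum is Σ d/(n(n−d)). With every d = 0 the sum is 0 and S(t) = 1.

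- Plain and log scales: S from 1 to 1, an event rate of 0% to 0%.
- Log-log scale: log(−log 1) does not exist. The logit and arcsine forms also fail, because they need 0/0.

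**What zero events allows.** The exact two-sided 95% upper limit is 1 − 0.025^(1/n).

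| n | Upper limit |
|---|---|
| 150 | 2.43% |
| 130 | 2.80% |
| 100 | 3.62% |

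Here 150 is the primary-phase enrolment and 130 is the plan's number evaluable for effectiveness at 12 months. The figure of 100 is an illustration, since the documents give no number at risk at 12 months. The two-sided Wilson limit at n = 150 is z²/(n + z²) = 3.84/153.84 = 2.50%.

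**How likely a zero is.** The documents give no expected rupture or conversion rate, so the rates in the first line are assumptions. Ignoring censoring, P(0 in 150) = (1 − r)^150:

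- r = 0.2%: 74%; 0.5%: 47%; 1%: 22%; 2%: 5%.
- All-cause death at the 3.4% average for endovascular repair in Section 2.1.3: 0.6%.
- Major adverse events at the plan's 11%: 2.6 × 10⁻⁸.

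The question therefore concerns rupture, conversion and possibly AAA-related death, not all five endpoints.

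**Would an exact interval at zero events, with everything else left alone, improve matters?** Compare it with one event in 150 and no earlier censoring:

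- Plain: 0.667% + 1.96 × √(0.00667 × 0.99333/150) = 0.667% + 1.302% = 1.97%.
- Log: 1 − 0.99333 × exp(−1.96 × √(1/(150 × 149))) = 1.96%.
- Log-log: 4.64%.

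Under plain or log, zero events would carry a higher upper limit (2.43%) than one event. At 12 months, zero events with 100 at risk gives 3.62%, above even two early events in 150 on the plain scale: 1.333% + 1.836% = 3.17%. The reversal between zero and one event in 150 disappears under log-log, but only if that scale is named as well.

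**The case for a change.** The best case for a change is that it costs one sentence and guards against a misleading line in a label. The plan chose a sound binomial limit for its primary endpoints, and that limit does not collapse: Formula 1 at p = 0 gives 1.645²/(150 + 1.645²) = 1.77%, one-sided. Section 10.4.1 has no such protection, and Section 10.9 does not list the topic. A rule fixed in advance is better than one chosen after a zero. Zeros are also more plausible at 30 days than at 12 months, because events by day 30 are a subset of those by 12 months.

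The gap in wording, the arithmetic and the preference for fixing the rule in advance all stand. They do not show that the plan is wrong. The interval form for a sparse descriptive table is the kind of detail that Section 10.9 defers, and a statistician who meets a blank or zero-width interval has a standard remedy. A zero rate shown with its denominator also lets any reader obtain the upper limit. Labeling is a possibility in Section 9.0, not a commitment.

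The single sentence is also less simple than it looks. It must fix the scale for one or more events. It must choose a 12-month denominator, and the number at risk at day 365 discards follow-up from subjects censored earlier. It must also say whether the 100 continued-access subjects count; with 250 subjects the limit at zero falls to 1.46%.

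**Conclusion.** No change to the plan follows. The omission is real but is ordinary missing detail in a descriptive analysis, which the later statistical analysis plan is there to fill. A 0% to 0% interval would appear only if a Greenwood default were used, an endpoint had no events, and the output were printed without thought. Even then the loss is an unreported upper limit of about 2.4% (0/150) to 2.8% (0/130) on rupture, conversion or possibly AAA-related death. No hypothesis, sample size or success criterion moves.

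This rests on the secondary endpoints staying untested, as Section 10.4 says, and on Section 10.9 being carried out. The chances of a zero for rupture and conversion rest on assumed rates. The author of the later plan may wish to name one interval form that stays coherent from zero events to one (for example log-log with events and exact binomial without), with its denominator and population. That is optional good practice, not a correction to this document.

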10.4.2 Assessment of Clinical Utility

Estimation of Mean Volume of Blood Loss

For each subject, the amount of blood loss is the outcome variable. The mean and standard deviation of blood loss values and 95% confidence intervals will be provided.

Estimation of Mean Duration of Procedure, Overall Hospital Stay

The objective is to estimate mean duration of procedure (minutes), mean time from hospital admission to discharge (days) and duration of anesthesia (minutes). For each outcome the mean, median, standard deviation and 95% confidence interval will be provided.

Anesthesia Type

The objective is to estimate the rate of general anesthesia use.

Vascular Access Type

The objective is to assess the rate of femoral vs. percutaneous access used. The rates will be presented as a percent with 95% confidence interval.

10.4.3 Effectiveness

All secondary effectiveness endpoints are categorical in nature. Technical success is only measured peri-operatively and will be presented as a percent with 95% confidence interval. All the remaining effectiveness endpoints will be presented by visit, as percents with 95% confidence intervals. Endoleak will be reported by type.

10.5 Assumption Verification

Visual inspection and statistical tests will be used to determine if the study variables are consistent with the assumptions of statistical tests proposed. For continuous variables, test of normality will be done by Shapiro-Wilks test or equivalent.

10.6 Study Retention and Handling of Missing Data

Every effort will be made to collect all data points in the study. The sponsor plans to minimize the amount of missing data by appropriate management of the prospective clinical trial, proper screening of study subjects, and training of participating investigators, monitors and study coordinators. Primary analyses will be performed on an intent-to-treat basis. All partial data that is available on subjects who drop out during the course of the study will be included.

In order to evaluate the effect of missing data on the primary outcomes a sensitivity analysis will be performed. The sensitivity analysis will include evaluating the primary outcomes using a best-case scenario (assuming missing data for the subjects are successes) a worse-case analysis (assuming all missing data for the subjects are failures), and a tipping point analysis as described by Yan 2009.² A multiple imputation analysis will also be performed using logistic regression to further evaluate the effect of missing data on the primary outcome (Little 2001).³

10.7 Poolability

Data will be pooled from multiple study sites for this analysis. The justification for pooling is made on a clinical basis (Meinert, 1986).⁴ This study will be conducted such that: 1) the same protocol will be used at each site; 2) site investigators and personnel will receive uniform training; and 3) central data management and monitoring will be applied with equal rigor at all

sites. The diversity of hospital and clinical practice settings will add to the scientific validity and generalizability of the findings. **Rates for the primary efficacy and safety endpoints will also be reported by clinical centers.**

10.8 Subject Populations for Analysis

Primary analysis will be performed on an intent-to-treat basis. The intent to treat group will include all subjects in which the delivery system is inserted into the access vessels.

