5.0 STUDY DESIGN

This is a Phase II prospective, consecutive enrolling, non-randomized multi-center clinical evaluation of the safety and effectiveness of the TriVascular Stent Graft when used in the treatment of patients with AAA.

A total of 150 subjects will be enrolled during the primary study phase with an additional 100 subjects enrolled during the continued access phase at up to 40 institutions. No one institution may enroll more than 30 subjects.

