5.4 Duration of Study

Subject follow-up visits will occur at one, six, and 12 months post implant procedure then annually through five years. Lifelong follow-up by the physician is required after subjects have completed the study.

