6.0 STUDY PROCEDURES

Treatment of subjects enrolled in this study will include tests and procedures listed in **Appendix IV: Schedule of Activities**. Placement of the AAA stent graft will be performed in accordance with the IFU.

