6.1 Patient Screening

Prospective candidates are evaluated in a consecutive manner for eligibility for the study at the time they are considered to be candidates for AAA repair. Initial screening may include diagnostic testing (e.g., imaging, angiogram, laboratory testing) performed as part of routine medical care.

The following steps outline the process to determine patient eligibility for enrollment and subsequent shipment of the device(s):

1. Ensure that patient has signed an IRB approved Informed Consent Form, per Institutional policies
2. Complete the Eligibility Verification Worksheet form
3. Complete the AAA Pre-Operative Sizing Worksheet
4. Fax #2 and #3 (above) to TriVascular Clinical Department [contact])
5. Submit contrasted spiral CT images to Core Lab obtained within 6 months of anticipated treatment.

Refer to Manual of Operations for Core Lab Imaging Guidelines.

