8.14 Technical Failures

In the event that an AAA stent graft could not be deployed due to a technical failure, contact TriVascular Clinical Affairs to obtain device return information. Device failure information will be captured on the **Device Failure eCRF**.

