9.1.2 Efficacy

The primary effectiveness endpoint is the proportion of subjects that achieve treatment success. Treatment success is a composite endpoint assessed at 12 months that requires all of the following criteria to be met in order for a subject to be considered a treatment success:

- Technical Success, defined as successful delivery and deployment of one aortic body and two iliac limbs.
- Freedom from Type I & III endoleak at 12 months
- Freedom from stent graft migration at 12 months
- Freedom from AAA enlargement at 12 months
- Freedom from AAA rupture and conversion to open repair through 12 months

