9.2.2 Stent Graft Efficacy

The following secondary efficacy endpoints will be assessed.

1) Technical Success

The physician was able to insert the delivery catheter and deliver an aortic graft and two iliac limbs to the treatment site.

2) AAA Enlargement

Any increase in aneurysm diameter (>5 mm) from the one month (baseline) post-operative measurement will be considered AAA enlargement, as determined by Core Lab.

3) Migration

Migration is defined as evidence of proximal or distal movement of the stent graft >10 mm relative to fixed anatomic landmarks. Spiral CT images will be used by Core Lab to determine migration from the one month (baseline) CT image.

4) Type I and III Endoleak

Type I and III endoleaks will be assessed by the Core Lab using Spiral CT images.

5) Device Integrity

The integrity of the stent graft will be evaluated from X-ray images by the Core Lab using the discharge X-ray as the baseline. Any fractured stents or other issues compromising the integrity of the stent graft will be reported.

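### Section 10.8 admits only subjects in whom the delivery system was inserted, so a failed insertion attempt, a treatment failure under 9.1.2 and 9.2.2, is outside the primary effectiveness denominator

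*Combined protocol and SAP*

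**What the plan says.** Sections 10.6 and 10.8 put the primary analyses on an intent-to-treat basis, and 10.8 defines that group: "The intent to treat group will include all subjects in which the delivery system is inserted into the access vessels".

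The effectiveness endpoint in 9.1.2 is a composite in which every component must be met. The first component is "Technical Success, defined as successful delivery and deployment of one aortic body and two iliac limbs". Section 9.2.2 describes technical success more fully: "The physician was able to insert the delivery catheter and deliver an aortic graft and two iliac limbs to the treatment site". Section 6.3 has the investigator record access success or failure at the procedure.

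On enrolment, section 5.0 says "A total of 150 subjects will be enrolled during the primary study phase" but not when a subject starts to count. Section 6.0 begins "Treatment of subjects enrolled in this study will include tests and procedures listed in", and 6.1 places eligibility for enrolment before device shipment. Both read as if enrolment comes before the procedure, but neither defines it.

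On follow-up, 5.4 says "Subject follow-up visits will occur at one, six, and 12 months post implant procedure then annually through five years". Section 8.14, which opens "In the event that an AAA stent graft could not be deployed due to a technical failure", covers device return and a device-failure form. Section 8.13 allows for conversion to open repair at the initial procedure and sets visits one month and one year after conversion.

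**The concern.** Entry to the primary set depends on passing part of the primary endpoint. Every analysed subject has met the insertion element by construction, and those who failed it are not counted. In a single-arm trial judged against a fixed 80% goal, no control arm loses comparable subjects, so the omission can act only in the device's favour. It also touches the second goal in section 1.0, which is to evaluate whether the system can be delivered.

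Nothing later in the plan restores these subjects. The best-case, worst-case, tipping-point and imputation analyses in 10.6 deal with missing data among subjects in the set. Section 10.9 promises a detailed SAP but no change of population. No set of all attempted or all enrolled subjects is defined.

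**Working it through.** **1. Who is affected.** There are three kinds of procedural failure.
- The catheter enters a vessel but cannot be advanced: in the set, counted as a failure.
- The catheter is advanced but the components are not all deployed: in the set, counted as a failure.
- Insertion is attempted and the system never enters a vessel: a failure under 9.2.2 and 9.1.2, but outside the set.

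Only the third kind is at issue.

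**2. The plan's own figure.** Inputs from 10.1.2 and 10.2: goal p0 = 0.80, assumed rate p1 = 0.882, n = 130, one-sided alpha 0.05. With the normal approximation,

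power = Φ{[(p1 − p0)√n − 1.645√(p0(1 − p0))] / √(p1(1 − p1))} = Φ{[0.082 × √130 − 1.645 × 0.4] / √(0.882 × 0.118)} = Φ(0.858) = 80.5%.

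The stated 80% is reproduced, so the sample-size calculation is not in question.

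**3. Pass mark.** Formula 2 in 10.3.2, with x successes among n and p = x/n:

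L = [2x + 1.645² − 1.645√(1.645² + 4x(1 − p))] / [2(n + 1.645²)].

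At n = 130, L(111) = 79.57% and L(112) = 80.43%. The test passes at 112 or more successes.

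**4. Adding back k excluded failures.** Successes stay at x and the denominator becomes 130 + k. Since x/(130 + k) ≤ x/130, the rate can only fall or stay the same.

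| Result in the 10.8 set | Lower limit | Smallest k that reverses it | With those failures included | Lower limit |
|---|---|---|---|---|
| 112/130 | 80.43% | 1 | 112/131 | 79.72% |
| 113/130 | 81.30% | 2 | 113/132 | 79.86% |
| 114/130 | 82.17% | 4 | 114/134 | 79.32% |
| 115/130 | 83.05% | 5 | 115/135 | 79.47% |

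The last row is close to the planned 88.2% (115/130 = 88.5%).

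**5. How many to expect.** The documents give no non-insertion rate. Assumed rates f of 0.5%, 1% and 2% give 150f = 0.75, 1.5 and 3 excluded subjects on average in 150 attempts. The chance of none, (1 − f)^150, is 47%, 22% and 5%. The literature table in 2.1.3 lists access/deployment failure at 0–11%, average 5.0%. That combines access with deployment failure, which 10.8 already counts, so it is only a loose upper guide.

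**6. Chance of passing when true success over all attempts is exactly 80%.** If every non-inserted subject is a failure, the rate among inserted subjects is 0.80/(1 − f). The exact binomial P(X ≥ 112 | n = 130) is:

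| f | Rate among inserted | Chance of passing |
|---|---|---|
| 0 | 80.0% | 4.6% |
| 0.5% | 80.4% | 5.7% |
| 1% | 80.8% | 7.1% |
| 2% | 81.6% | 10.9% |

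**7. Chance that the exclusion decides the result, given that such subjects exist.** With one excluded failure the pass mark over all attempts is 113/131 (L = 80.57%), so the conclusion changes only at X = 112. That has probability 1.9%, 10.1% and 7.9% at true inserted rates of 80%, 86% and 88.2%. With two, the pass mark is 114/132 (L = 80.71%), and X = 112 or 113 has probability 3.1%, 19.9% and 17.2%.

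**8. Safety.** The largest passing count with Formula 1 is 23/150 (upper limit 20.78%, goal 21%). Adding one subject with a major adverse event gives 24/151, 21.38%, a fail. Adding one without gives 23/151, 20.65%, still a pass. The effect can go either way.

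**The case against.** The strongest reply is that the group is very small. Section 10.8 starts at insertion, not at deployment or implantation, so most technical failures are kept. Inclusion criterion 6 and the sizing worksheet and CT submission in 6.1 screen for access. At the planned rate a typical result has room to spare: five exclusions are needed at 115/130, against 0.75 to 3 expected under the assumed rates. All of this stands and limits the size of the point.

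A reader might infer that the test's error rate is inflated. The documents do not support that outright. For the population that 10.8 defines, the exact error stays 4.6%. The higher figures hold only if the 80% goal is meant for all attempted subjects, and 10.1.2 gives neither a source nor a denominator for it.

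A reader might also infer that enrolled subjects are dropped. The protocol never says when enrolment occurs. If it occurs at insertion, the 10.8 set equals the enrolled set, although every analysed subject would still have met the insertion element by construction.

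Nor do the documents show that the safety result favours the device, or that these subjects go entirely unfollowed. Sections 6.3 and 6.4 collect adverse events at the procedure and before discharge, and 8.13 may cover those converted at the initial procedure. Section 8.6, however, defines conversion for implanted subjects, so that cover is uncertain, and a failed-insertion subject who is not converted has no stated schedule.

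The detailed SAP under 10.9 is a natural place to settle this, but nothing commits it to do so.

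**Conclusion.** The point holds for effectiveness. By the plan's own definitions a failed insertion attempt is a treatment failure, and 10.8 leaves it out of the primary denominator. The direction is certain: the success rate is raised or left unchanged. The size is unknown and probably small. It could decide a result at or just above 112/130 and is unlikely to matter well above it. The calculations assume 130 evaluable inserted subjects, every failed insertion counted as a failure, and non-insertion rates of 0.5% to 2% that are not in the documents. For the 30-day safety endpoint the set should be made consistent, but no direction of bias is shown. This should be fixed; it does not undermine the design.

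**What to change.** Replace the 10.8 definition with wording such as: *The primary analysis set is all primary-phase subjects in whom insertion of the delivery system was attempted, whether or not it entered an access vessel. Subjects in whom insertion failed are technical failures and treatment failures.* State what counts as an attempt and when a subject counts as enrolled. Report the present inserted-only set as supportive.

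Use the same set for the 30-day major adverse event rate, and align the safety population in 10.1.1, now worded as those receiving the stent graft, with it. State how 30-day status is obtained for failed-insertion subjects not already followed under 8.13.

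The cost is wording, to be settled before database lock. Access success or failure is already recorded under 6.3, so the subjects can be identified. The downside is a slightly lower reported success rate if any such subjects exist, and 30-day status to be obtained for a few of them. If there are none, the results do not change.
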